#### **8.5.2 Primary Safety**

Any adverse events and serious adverse events related to the use of the investigational device will be analyzed with descriptive statistics and nominal 95% confidence interval. There will be no formal statistical hypothesis test for primary safety.

### **8.6 Secondary Endpoints**

The following secondary endpoints will provide additional characterization of the Connected Catheter in the treatment of chronic Urinary Retention and to support potential labeling claims.

1. Successful device insertion, anchoring, and removal
2. Successful sealing of the Connected Catheter valve
3. Quality of life improvement as measured by SCI-QOL Survey and other surveys
4. UTI occurrence rate
5. Lower Urinary Tract injury rate

These endpoints will be analyzed with descriptive statistics and nominal 95% confidence interval.

### **8.7 Subject Selection**

Only subjects who meet all inclusion criteria and no exclusion criteria, agree to comply with the follow-up visit schedule and provide informed consent will be eligible to be treated and participate in the study. If a subject moves away during the study, every effort should be made to maintain

the follow-up schedule including having an appropriate physician follow the subject.

### 8.7.1 Inclusion Criteria

1. Males  $\geq$  18 years old diagnosed with chronic Urinary Retention
2. Must be clinically suitable and capable of safely managing bladder using an intermittent voiding or indwelling strategy
3. Must have stable urinary management history as determined by the Investigator

OR:

4. Must have urodynamic profile suitable for the Connected Catheter (including bladder capacity  $\geq$  200mL without uninhibited bladder contractions)
5. Subject's lower urinary tract anatomy must fall within the ranges serviceable by the Connected Catheter device, as specified in the Investigational Device Instructions For Use.

### 8.7.2 Exclusion Criteria

1. Active symptomatic urinary tract infection, as defined in this protocol (*subjects may receive the device after UTI has been treated*)
2. Significant risk profile or recent history of urethral stricture (e.g. stricture within past 90 days)
3. Significant risk profile or recent history of clinically significant (uncontrolled) autonomic dysreflexia
4. Significant intermittent urinary incontinence (between catheterizations)
5. Uninhibited bladder contractions and/or Vesicoureteral reflux that is not reliably controlled with medication or alternate therapy (e.g. Botox injection)
6. Pre-existing urinary pathologies and/or morphological abnormalities of the lower urinary tract or bladder (assessed during in-depth medical screening, including cystoscopy and urine analysis)
7. Urinary tract inflammation or neoplasm
8. Urinary fistula
9. Bladder diverticulum (outpouching)  $>$  5cm in size
10. Chronic pyelonephritis (secondary to upper urinary tract infection(s) within past 6 months)
11. Impaired kidney function or renal failure
12. Active gross hematuria
13. Active urethritis
14. Bladder stones
15. Dependence on an electronic medical implant (e.g. cardiac pacemaker or implanted drug pump) or external device

16. Any unsuitable comorbidities as determined by the Investigator or complications related to use of certain medications
17. Any physical or cognitive impairments that diminish the subject's ability to follow directions or otherwise safely use the Connected Catheter System
18. Catheter Assessment Tool screening yields unacceptable results

### **8.8 Number of Sites and Sample Size**

Up to 4 sites in the United States are planned for this study.

The number of subjects to be enrolled in the study (ITT) as defined by EN ISO 14155; is 36 subjects. Of these, it is expected only 24 of the subjects will be found to meet the basic eligibility criteria to be tested for device tolerability screening.

Assuming a 33% dropout after the device tolerability screening, the final number of evaluable subjects required is a minimum of 16 subjects (See 10.1).

### **8.9 Study Duration**

Each subject will enter the study for 6 weeks after passing the Device Tolerability Screening. The study duration to complete enrollment, monitor and collect the data is anticipated to be 12 months.

### **8.10 Site and Physician Selection**

Sites will be selected based on the availability of the subject pool to be included in the study and the sites' ability to perform the research in compliance with FDA regulations and guidelines and applicable international standards and regulations.

The sites and physicians are required to comply with FDA regulations and guidelines and applicable international standards and regulations (the definition of subject enrollment is per this clinical investigation protocol). In addition, the sites must be able to comply requirements specified by the central institutional review boards (IRB) or ethics committees (EC) and / or the sites respective IRB or EC.

Physicians selected must have experience in performing cystoscopies and treating Urinary Retention and other urological conditions for adult males. Selected physicians will be trained in the use of the Gen 2 Connected Catheter System and Accessories prior to enrolling subjects. The principal investigator will ensure that only trained sub-investigators who satisfy the physician selection criteria can perform any part of the study interventional procedure.

Healthcare professionals or site staff that assist or perform the follow-up evaluations do not need to be trained on the use of the Gen 2 Connected Catheter System and Accessories, but must be delegated and trained to perform the follow-up visit procedures.

## **9 STUDY PROCEDURE**

Throughout the study, any urinary or other health issues potentially related to use, and requiring medical attention, will be treated according to Standard of Care. Table 9-2 outlines the evaluations completed during each visit. The site may pre-screen potential subjects by reviewing medical records to identify potential study subjects. Once identified, these subjects are approached to discuss the study, asked to participate and sign the IRB approved informed consent form. The site

may not initiate any study-specific (non-standard of care) procedures without first obtaining informed consent.

### 9.1 Informed Consent Procedure

Written Informed Consent must be obtained for each prospective subject before any study- specific tests or screening procedures are performed on that subject. The informed consent process must be performed by the Principal Investigator (PI) or their authorized designee. They will be responsible for ensuring subjects understand all relevant aspects of the study.

### 9.2 Eligibility Screening

Eligibility screening of prospective subjects will be conducted by a Site Investigator and/or a designated Research Coordinator. Subjects who wish to enroll will undergo the following assessments at Screening Appointment. The subject will sign an Informed Consent Form administered by a designated Principal Investigator or authorized designee.

Subject eligibility will be assessed on the basis of Screening Appointment data, according to the eligibility criteria listed above.

**Table 9-1: Subject Screening Criteria**

Evaluation	Accepted interval prior to Eligibility Screening Appointment (unless specified otherwise)	Condition
Informed consent	Within 30 days prior	Prior to any study-specific procedures
General Medical Evaluation a. baseline vitals b. physical examination c. Lower Urinary Tract (LUT) function and measurements	Within 30 days prior	Evaluation is complete and adequately documented in report for assessment
Medical History a. Date and etiology of Urinary Retention diagnosis b. Review of past medical history (neurological, urological and systemic)	Within 30 days prior	Evaluation is complete and adequately documented in report for assessment

Evaluation	Accepted interval prior to Eligibility Screening Appointment (unless specified otherwise)	Condition

 
c. Urinary management history: method(s) of bladder management and dates of major changes
 
d. History of urinary complications (UTIs, false passage, stricture, etc.)
 
e. Level and severity of spinal cord injury (if applicable; including ASIA Score, if known by subject)
 
		
Lower Urinary Tract Evaluation – visual evaluation of lower urinary tract, and baseline anatomical measurements.	Within 30 days prior	Evaluation is complete and adequately documented in report for assessment
Catheter Assessment Tool (CAT) Evaluation	Within 30 days prior	Evaluation is complete and adequately documented in report for assessment
Baseline Urinalysis and Urine Culture	Within 30 days prior	If the patient has a UTI (bacteriuria $\geq 10^5$ CFU per mL, plus at least one NIDRR consensus-defined symptom), they must undergo treatment before the initial insertion.
Voiding Characterization 
 
a. Pre-Void Bladder Volume – measured by ultrasound
 
b. Voided urine volume
 
c. Post-Void Residual Volume – measured by ultrasound
 
	Within 30 days prior	Bladder must contain at least 200 mL of urine before conducting the test.

Evaluation	Accepted interval prior to Eligibility Screening Appointment (unless specified otherwise)	Condition
Bladder Management SCI-QOL Survey (short form)	Within 30 days prior	Evaluation is complete and adequately documented in report for assessment
Current Catheter Experience Survey	Within 30 days prior	Evaluation is complete and adequately documented in report for assessment
USQNB-IC Survey	Within 30 days prior	Evaluation is complete and adequately documented in report for assessment
Medications	Within 30 days prior	All medications taken are properly documented.

All subjects screened for this study will be captured on the site's Screening and Enrollment Log, which will record at a minimum, the prospective subject's ID #, subject's initials, date of screening and the reason(s) for study exclusion (if applicable). The Screening and Enrollment Log will use numeric subject identifier numbers.

### 9.2.1 Insertion and Initial Voiding Assessment

The Insertion Procedure is to begin with the insertion of the Connected Catheter using the IR Tool, according to device training procedures and Instructions for Use (IFU). The initial insertion will be performed by a trained clinician. Once the Connected Catheter has been placed, a urine sample will be collected and sent out for urinalysis and urine culture. Note that the subject must have at least 200 mL of urine in the bladder, as measured by ultrasound, prior to voiding and sample collection. After the bladder is emptied, a member of the research team (physician, nurse, etc.) will measure PVR volume using an ultrasound bladder scanner and record this reading.

### 9.2.2 User (Subject) Training

A trained, designated member from the Sponsor or a trained member of Study Site's research team will instruct the subject on how to use the Connected Catheter - insertion, bladder voiding, and removal - using a training model. A short, initial training will take place before insertion of the Connected Catheter and will continue intermittently throughout the Insertion Appointment, in between the positioning and sizing assessment, as well as between voiding cycles, until the subject demonstrates proficiency in Connected Catheter insertion, voiding, and removal procedures to the research staff. If the subject is unable to demonstrate proficiency in the Connected Catheter voiding

or removal procedure, then he may be allowed to complete the Clinic Assessment, but not allowed to proceed to the Test Phase. Each subject will be requested to refrain from sexual activity until the first follow-up appointment (up to 7 days). After the first Connected Catheter use is completed, the subjects will be informed that normal sexual activity may occur with caution. Device performance and impact on sexual will be evaluated in the Connected Catheter Safety and Performance Survey administered during each appointment where the device is replaced.

### **9.2.3 Device Positioning and Sizing Assessment**

The subject will undergo a positioning and sizing assessment to evaluate if any migration of the Connected Catheter has occurred in the lower urinary tract by performing a set of mobility maneuvers intended to simulate the subject's activities of daily living. These maneuvers will be tailored to the subject's physical ability level (e.g. ambulatory vs. non-ambulatory) and will include common motions such as walking (or wheeling), sit-to-stand transitions, ascending and descending stairs as applicable to each subject. Any observed instances of Connected Catheter migration will be recorded. If an observed instance of migration is suspected to be due to incorrect sizing, the Connected Catheter may be removed, and a different size inserted (per IFU).

### **9.2.4 Bladder Filling Period**

In between voiding cycles, the subject is to remain in the vicinity of the study site until voiding urgency is felt or the scheduled timed void(s) has occurred. During this bladder filling period, the subject should consume adequate fluids (>300 mLs) to promote bladder filling. The bladder must contain at least 200 mL of urine, as measured by ultrasound, before performing the voiding assessment. Subjects must consume fluid until the required minimum volume of urine in the bladder is achieved.

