**Table 7-1: Major Risks for the Connected Catheter**

Risk	Description
Urinary Tract Infection (UTI)	UTI is defined in this protocol as bacteriuria $\geq 10^5$ CFU per mL, plus at least one NIDRR consensus-defined symptom. If infection is suspected, appropriate diagnostic and therapeutic measures should be taken.
Asymptomatic Bacteriuria	The presence of bacteria in the properly collected urine of a patient that has no signs or symptoms of a urinary tract infection.
Bladder Spasms	When the bladder muscle squeezes suddenly without warning, causing an urgent need to release urine. The spasm can force urine from the bladder, causing leakage.
Dysuria	Pain experienced while urinating. Dysuria can be caused by UTI, inflammation of the LUT, sexually transmitted diseases, and more. The operation of the device should not cause pain while voiding. If this occurs, a clinician should evaluate the subject to determine the likely cause and follow the standard of care. If necessary, the device may be removed.
Genitourinary pain	Initial discomfort may occur when first using the device. Pain should be properly evaluated by a clinician and the cause(s) identified. Genitourinary pain can have many causes unrelated to the device itself ranging from enlarged prostate to fibromyalgia to infection. The proper standard of care should be followed once the cause(s) are identified.

Risk	Description
Hematuria	Blood in the urine may be caused by LUT injury, UTI, kidney or bladder stones, enlarged prostate, the device itself (from insertion, removal, migration, improper sizing), and more. During initial use of the device minor hematuria may be observed. If it continues or worsens, then follow the standard of care to diagnose and alleviate the symptom.
Stricture	Hardening of the tissue. May be caused by frequent catheter use and/or false passage.
Urethral Trauma	False passage may be associated with improper and/or frequent catheter use.
Urinary Incontinence	Leaking may occur through or around the catheter if the bladder spasms, or the catheter valve is not closed properly.
Urinary retention	If patient is unable to empty the bladder, then Urinary Retention may occur.
Discomfort	Discomfort is often associated with frequent catheterization.

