### **8.5 Primary Endpoints**

#### **8.5.1 Primary Efficacy**

During each follow-up, and during the initial device insertion and evaluation, the Post-Void Residual (PVR) urine volume will be measured via ultrasound.

A subject will be considered a responder to the device if at least 80% of the subject's available PVR values are:

- a. Less than 50 mL OR
- b. Equal or less than baseline PVR with the standard urinary management system

If a subject drops out before the conclusion of the study after passing the Device Tolerability Screening, their PVR data will still be included in the primary analysis.

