## **9.4 Test Phase**

The Test phase will require three (3) Exchange Appointments and a final Removal Appointment. Each appointment will assess PVR, voided volume, quality-of-life (QOL), and urinary tract injury, adverse events, medication, and other study assessment. Additionally, the subjects will be asked to fill out a User Experience Survey and Safety and Performance Survey and the device will be evaluated for fit, migration, placement, and removal.

At each exchange visit, the clinic research staff will follow these procedures:

1. Patient Arrival – Vital Signs and other measurements
2. Bladder Volume – Measurement using Ultrasound to ensure at least 200 mL of urine
3. Patient empties bladder – PVR volume measurement using Ultrasound
4. Patient removes Connected Catheter
5. Patient waits for bladder to fill – additional surveys completed
6. Patient inserts new Connected Catheter and bladder emptied – PVR volume measured
7. Patient Departure

For the final device removal visit the clinic research staff will follow these procedures:

1. Patient Arrival – Vital Signs and other measurements
2. Bladder Volume – Measurement using Ultrasound to ensure at least 200 mL of urine
3. Patient empties bladder – PVR volume measurement using Ultrasound
4. Patient removes Connected Catheter
5. Patient completes all surveys
6. Patient departure

Once the patient completes the final device removal visit the patient will enter the follow-up phase.

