## 10 STATISTICAL CONSIDERATIONS

### 10.1 Primary Endpoint Hypothesis

The primary endpoint analysis consists of a one-sided test of the null hypothesis that no more than 60% of users are responders to the device against the alternative that more than 60% of users are responders, as given below:

$$H_0: R \leq 60\%$$

$$H_a: R > 60\%$$

Where,

R = % of users who are responders

In this study, R is estimated as the percent of subjects who are responders, and a subject will be considered a responder to the device if at least 80% of that subject's individual available PVR values are:

- a. Less than 50 mL OR
- b. Equal or less than baseline PVR with the subject's standard urinary management system

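### A scheduled PVR reading that cannot be taken because the worn catheter leaks drops out of the responder denominator, and no rule says how to score it

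*Combined protocol and SAP*

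**What the plan says.** **The volume condition.** Section 9.2.4 states: "The bladder must contain at least 200 mL of urine, as measured by ultrasound, before performing the voiding assessment". For a bladder still below that volume the only instruction is "Subjects must consume fluid until the required minimum volume of urine in the bladder is achieved". There is no time limit and no rule on what to record if 200 mL is never reached. Section 9.4 repeats the check before the worn-catheter reading at each exchange visit and at the removal visit: "Bladder Volume – Measurement using Ultrasound to ensure at least 200 mL of urine".

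**The scoring rule.** Section 8.5.1 sets the occasions: "During each follow-up, and during the initial device insertion and evaluation, the Post-Void Residual (PVR) urine volume will be measured via ultrasound". Section 10.1 makes a man a responder if "at least 80% of that subject's individual available PVR values are" below 50 mL, or no higher than his baseline under his standard management. Neither section sets a minimum number of readings or says how to treat one that could not be obtained.

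**The foreseen failure.** Table 7-1 lists it among the major risks: "Leaking may occur through or around the catheter if the bladder spasms, or the catheter valve is not closed properly". Valve sealing is a secondary endpoint (8.6) and part of the weekly assessment (Table 9-2). It is summarised descriptively and does not enter the responder definition.

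**Missing data.** Section 10.3 promises tipping-point analyses for missing data without naming the unit (subject or single reading) or the rule.

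**The concern.** A catheter that does not hold urine can keep the bladder from reaching the volume at which a reading may be taken. The reading is then missing because of the device, and the available-values rule removes it from numerator and denominator alike.

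The order of steps at an exchange visit adds to this. The old catheter is removed, the bladder fills, the new catheter is inserted and the bladder is emptied through it (9.4, steps 4 to 6). That second reading follows filling with no catheter in place, so it cannot show that the worn catheter leaked, and it enters the score as usual.

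Section 6 says the study is designed to show that the device drains the bladder and lets the patient control voiding. What is at stake is whether the tested responder rate reflects that claim in men whose catheters leak at scheduled visits but who stay in the study.

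**Working it through.** **1. Subject numbers.** Section 8.8 sends 24 men into tolerability screening and assumes 33% dropout: 24 × (1 − 0.33) = 16.08, so the stated 16 evaluable subjects reproduce. No power is stated, so there is none to reproduce.

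**2. Responders needed.** Section 10.3 uses an exact binomial test, one-sided at 0.05, null rate 0.60. With n = 16:
- P(X ≥ 13 | 0.60) = 0.065, not significant
- P(X ≥ 14 | 0.60) = 0.018, significant

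Fourteen responders are needed. At a true rate of 0.90 (section 10.2 expects more than 90%) the power is 0.789. One man's status separates 13/16 from 14/16.

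**3. Scheduled readings per completer.** Three at insertion (9.2.5), two at the end of tolerability screening (9.3 calls for the Test Phase assessments; two readings is my reading of that), two at each of three exchange visits, and one at removal (9.4): 3 + 2 + 3 × 2 + 1 = 12. Section 9.2.5 gives two cycles at every Test Phase visit, which would make it 13; the two sections should be reconciled. Five readings are on a worn catheter: day 7, three exchanges, removal.

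**4. One man, all other readings passing.**

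| Worn-catheter readings lost | As written | Lost counted as not met, of 12 | Of 13 |
|---|---|---|---|
| 2 | 10/10 (11/11), responder | 10/12 = 83.3%, responder | 11/13 = 84.6%, responder |
| 3 | 9/9 (10/10), responder | 9/12 = 75.0%, non-responder | 10/13 = 76.9%, non-responder |
| 5 | 7/7 (8/8), responder | 7/12 = 58.3%, non-responder | 8/13 = 61.5%, non-responder |

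With everything else passing, status changes only from the third lost reading on.

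**5. Illustrative range.** Assume each of the five worn-catheter readings is lost independently with probability q and every reading taken passes with probability 0.97. Lost readings L ~ Binomial(5, q); passes among the 12 − L taken ~ Binomial(12 − L, 0.97). A man responds if passes are at least 80% of 12 − L (as written) or of 12 (lost counted as not met). The last column is P(X ≥ 14 | n = 16) at the counted responder chance.

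| q (assumed) | Responder, as written | Responder, lost counted as not met | Chance of ≥ 14/16, counted |
|---|---|---|---|
| 2% | 99.5% | 99.1% | > 99.9% |
| 5% | 99.5% | 98.1% | 99.7% |
| 10% | 99.5% | 95.6% | 97% |
| 20% | 99.5% | 87.0% | 65% |
| 30% | 99.3% | 74.0% | 17% |

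As written, the chance of at least 14/16 stays near 100% throughout. With 13 scheduled readings the counted responder chances at 10%, 20% and 30% are 95.1%, 86.2% and 73.1%.

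**The case against.** **The plan means the reading to be obtained.** No section says the worn-catheter reading is skipped and the catheter simply exchanged. The man is to keep drinking, and under section 14.8.3 an omitted required test is a protocol deviation. This stands: a reading is lost only if drinking fails or is abandoned. A deviation form, however, records the loss without scoring it.

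**A leaking bladder may well have a low residual.** A reader might infer that men with failing devices are counted as responders when their PVR would have failed, so that the rate is biased upward. The documents do not support that. Such readings, if taken, might have passed, and dropping the volume condition would not cure the problem. Counting them as not met adds a sealing element to a PVR endpoint. That is a choice, and its justification is the claim in section 6.

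**Leaking men may be screened out.** Exclusions for significant incontinence and uncontrolled contractions (8.7.2), and the need to use the device successfully in the tolerability week (9.3), will remove some. But the discharge criteria in 9.2.7 name insertion, voiding and anchoring, not sealing, and a leak can start later. A man who leaks continuously and still completes the study is an extreme case that the documents give no reason to expect.

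**Missing data are already addressed.** Section 10.3 could cover this, but its unit is unstated. A man with other readings already has a responder status, so an analysis by subject would not treat him as missing.

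**The rates are assumed.** True. Moreover, q is the chance of losing a reading, not of a leak; an intermittent or slow leak may still allow 200 mL.

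**Conclusion.** The gap in the endpoint definition is real: a scheduled reading that leakage makes unobtainable has no scoring rule, and the available-values wording removes it. Three such losses out of 12 turn a 75% non-responder into a 9/9 responder, and at n = 16 one man can move the result across the 14-responder threshold.

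How much this matters in practice cannot be judged from the documents, which give no leak rate. Under the model above, with independent losses and a 97% pass rate, the effect is negligible at 2% to 5% lost and large only at about 20% or more. The point concerns what the responder rate can be said to show about drainage and controlled voiding. It is not evidence of a bias in PVR, nor that many leaking men would be scored as responders. A man with no available reading at all would have an undefined status and would not count as a responder by default.

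**What to change.** 1. Add a CRF field giving the reason whenever 200 mL is not reached at a scheduled assessment.
2. State in 8.5.1 and 10.1 that a scheduled reading not obtainable because the catheter in place leaks counts as not meeting the PVR criterion.
3. Report the responder rate with those readings left out as a sensitivity analysis.
4. Specify in 10.3 that the tipping-point analysis also works at the level of single readings.

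This changes scoring and recording only; the 200 mL condition and the visit procedures stay as they are. The cost is a sentence in each of the two endpoint sections, one in 10.3 and one CRF field. The downside is a possibly lower responder rate, by an amount that depends on how often readings are lost. The rule should be set before data are seen, because a later choice could look driven by the results.
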